## 8.5 Hospitalization

Adverse events reported from studies associated with hospitalization or prolongations of hospitalization are considered serious. Any initial admission (even if less than 24 hours) to a healthcare facility meets these criteria. Admission also includes transfer within the hospital to an acute/intensive care unit (e.g., from the psychiatric wing to a medical floor, medical floor to a coronary care unit, neurological floor to a tuberculosis unit).

Hospitalization does not include the following:

- Rehabilitation facilities;
- Hospice facilities;
- Respite care (e.g., caregiver relief);
- Skilled nursing facilities;
- Nursing homes;
- Routine emergency room admissions;
- Same day surgeries (as outpatient/same day/ambulatory procedures).

Hospitalization or prolongation of hospitalization in the absence of a precipitating, clinical AE is not in itself a SAE. Examples include:

- Admission for treatment of a preexisting condition not associated with the development of a new AE or with a worsening of the preexisting condition (e.g., for work-up of persistent pre-treatment laboratory abnormality);
- Social admission (e.g., subject has no place to sleep);
- Administrative admission (e.g., for yearly physical examination);
- Study-specified admission during a study (e.g., for a procedure required by the study protocol);
- Hospitalization for observation without a medical AE;
- Optional admission not associated with a precipitating clinical AE (e.g., for

- elective cosmetic surgery);
- Pre-planned treatments or surgical procedures should be noted in the baseline documentation for the entire study and/or for the individual subject;
- Admission exclusively for the administration of blood products.

Diagnostic and therapeutic non-invasive and invasive procedures, such as surgery, should not be reported as AEs; however, the medical condition for which the procedure was performed should be reported if it meets the definition of an AE. For example, an acute appendicitis that begins during the AE reporting period should be reported as the AE, and the resulting appendectomy should be recorded as treatment of the AE.

## 8.6 Severity Assessment

All AEs must be graded according to CTCAE v5.0

(<http://ctep.cancer.gov/reporting/ctc.html>).

GRADE	Clinical Description of Severity
0	No Change from Normal or Reference Range
1	MILD Adverse Event
2	MODERATE Adverse Event
3	SEVERE Adverse Event
4	LIFE-THREATENING OR DISABLING Adverse Event
5	DEATH RELATED TO Adverse Event

A severe event is not necessarily a serious event. For example, a headache may be severe (interferes significantly with subject's usual function) but would not be classified as serious unless it met one of the criteria for SAEs, listed above.

## **8.7 Causality Assessment**

The investigator's assessment of causality must be provided for all AEs (serious and non-serious); the investigator must record the causal relationship in the CRF, as appropriate, and report such an assessment in accordance with the SAE reporting requirements if applicable. An investigator's causality assessment is the determination of whether there exists a reasonable possibility that the investigational product caused or contributed to an AE; generally the facts (evidence) or arguments to suggest a causal relationship should be provided. If the investigator does not know whether or not the investigational product caused the event, then the event will be handled as "related to investigational product" for reporting purposes, as defined by the Sponsor (see Section 8.11). If the investigator's causality assessment is "unknown but not related to investigational product", this should be clearly documented on study records.

In addition, if the investigator determines a SAE is associated with study procedures, the investigator must record this causal relationship in the source documents and CRF, as appropriate, and report such an assessment in accordance with the SAE reporting requirements, if applicable.

## **8.8 Exposure During Pregnancy**

For investigational products, an exposure during pregnancy (also referred to as exposure in-utero [EIU]) occurs if:

- A female becomes, or is found to be, pregnant either while receiving or having been directly exposed to (e.g., environmental exposure) the investigational product, or the female becomes, or is found to be, pregnant after discontinuing and/or being directly exposed to the investigational product (maternal exposure);
- A male has been exposed, either due to treatment or environmental, to the

investigational product prior to or around the time of conception and/or is exposed during his partner’s pregnancy (paternal exposure).

If any study subject or study subject’s partner becomes, or is found to be, pregnant while receiving the investigational product or within 28 days of the last treatment on study, the investigator must submit this information to drug provider on an Exposure-in-Utero Form. In addition, the investigator must submit information regarding environmental exposure to lorlatinib in a pregnant woman (e.g., a nurse reports that she is pregnant and has been exposed to a cytotoxic product by inhalation or spillage) using the Exposure-in-Utero Form. This must be done irrespective of whether an AE has occurred and within 24 hours of awareness of the pregnancy. The information submitted should include the anticipated date of delivery (see below for information related to induce termination of pregnancy).

Follow-up is conducted to obtain pregnancy outcome information on all EIU reports with an unknown outcome. The investigator will follow the pregnancy until completion or until pregnancy termination (i.e., induced or spontaneous abortion) and then notify drug provider of the outcome. The investigator will provide this information as a follow up to the initial Exposure-in-Utero Form. The reason(s) for an induced abortion should be specified. An EIU report is not created when an ectopic pregnancy report is received since this pregnancy is not usually viable. Rather, a SAE case is created with the event of ectopic pregnancy.

If the outcome of the pregnancy meets the criteria for immediate classification as a SAE (i.e., spontaneous abortion, stillbirth, neonatal death, or congenital anomaly [including that in an aborted fetus, stillbirth or neonatal death]), the investigator should follow the procedures for reporting SAEs.

In the case of a live birth, the “normality” of the newborn can be assessed at the time of birth (i.e., no minimum follow-up period of a presumably normal infant is required before an Exposure-in-Utero Form can be completed). The “normality” of an aborted

fetus can be assessed by gross visual inspection, unless pre-abortion test findings are suggestive of a congenital anomaly.

Additional information about pregnancy outcomes that are classified as SAEs follows:

- “Spontaneous abortion” includes miscarriage and missed abortion;
- All neonatal deaths that occur within 1 month of birth should be reported, without regard to causality, as SAEs. In addition, any infant death after 1 month that the investigator assesses as possibly related to the exposure during pregnancy to the investigational medication should be reported.

Additional information regarding the exposure during pregnancy may be requested by the investigator. Further follow-up of birth outcomes will be handled on a case-by-case basis (e.g., follow-up on preterm infants to identify developmental delays). In the case of paternal exposure, the investigator will provide the study subject with the Exposure-in-Utero Pregnant Partner Release of Information Form to deliver to his partner. The investigator must document on the Exposure-in-Utero Form that the subject was given this letter to provide to their partner.

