- Patients who are investigational site staff members directly involved in the conduct of the study and their family members, site staff members otherwise supervised by the Investigator, including their family members, directly involved in the conduct of the study.
- Pregnant female patients; breastfeeding female patients; fertile male patients and female patients of childbearing potential who are unwilling or unable to use a highly effective method of contraception as outlined in this protocol for the duration of the study and for at least 97 days, if male or 35 days if female, after the last dose of investigational product under lorlatinib.

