## **8.1 Reporting Period**

For SAEs, the active reporting period to the investigator or its designated representative begins from the time that the subject provides informed consent, which is obtained prior to the subject's participation in the study, i.e., prior to undergoing any study-related procedures and/or receiving investigational product, through and including 28 calendar days after the last administration of the investigational product regardless of the start of any subsequent cancer therapy. SAE should be reported via the CRF in the active reporting period. Following the active safety reporting period, other SAEs of which the investigator becomes aware should be reported to drug provider, unless the SAE is attributed by the investigator to complications of either the underlying malignancy or any subsequent anti-cancer therapy or to the patient's participation in a subsequent clinical study.

Non-serious adverse events should be recorded on the CRF from the time the subject has taken at least one dose of study treatment through last subject visit.

If a subject begins a new anticancer therapy, the AE reporting period for non-serious AEs ends at the time the new treatment is started.

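### Mandatory pregnancy reporting stops 28 days after the last treatment, short of the protocol's own contraception period for both sexes and narrower than Section 8.8's own exposure definitions

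*Protocol*

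**What the plan says.** Protocol Section 8.8 sets the reporting duty. It begins "If any study subject or study subject’s partner becomes, or is found to be, pregnant while receiving the investigational product" and continues "or within 28 days of the last treatment on study". The form goes to the drug provider within 24 hours of awareness, whether or not there has been an adverse event. Reports whose outcome is unknown are then followed to the end of the pregnancy.

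The definitions at the start of the same section have no day limit. Maternal exposure includes the case where "the female becomes, or is found to be, pregnant after discontinuing and/or being directly exposed to the investigational product (maternal exposure"). Paternal exposure covers a man exposed to the "investigational product prior to or around the time of conception and/or is exposed during his partner’s pregnancy (paternal exposure").

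The last exclusion criterion in Section 4.2 excludes fertile patients who will not or cannot use highly effective contraception during the study and "for at least 97 days, if male or 35 days if female, after the last dose of investigational product".

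Section 8.1 runs the active period for serious adverse events "through and including 28 calendar days after the last administration of the investigational product regardless of the start of any subsequent cancer therapy". For the time after that it adds: "Following the active safety reporting period, other SAEs of which the investigator becomes aware should be reported to drug provider", with exceptions for events attributed to the malignancy, to later anticancer therapy or to a later trial.

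**The concern.** The protocol asks men to avoid conception for more than three months after the last dose and women for five weeks. For both, the duty to report a pregnancy ends at four weeks. A site that follows Section 8.8 exactly would submit no form for a pregnancy beginning on day 29 or later, even though contraception was still required and the section's own definitions count it as an exposure.

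The site may well learn of such a pregnancy. Surgery is planned within 6 weeks of the last dose, and follow-up runs to 1 month after surgery (Sections 3.1 and 6.4.7). The schedule of activities places a repeat pregnancy test at the visit headed by completion of surgery.

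What is at stake is the completeness of pregnancy-exposure data: the form and, through it, follow-up of the pregnancy to its outcome. The efficacy analysis is not involved.

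**Working it through.** The protocol gives no figure to reproduce; the check compares its periods.

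**Inputs**
- Reporting trigger: 28 days after the last treatment, for subjects and partners alike (Section 8.8).
- Contraception period after the last dose: at least 97 days for men, 35 days for women (Section 4.2).
- Last dose to surgery: planned within 6 weeks, or 42 days (Section 3.1).
- End of follow-up: 1 month after surgery (Section 6.4.7), taken here as 30 days.

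**Step 1. Time without a mandatory report**, counting both periods from the last dose. Uncovered days = contraception period − 28; share = uncovered days ÷ contraception period.

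| | Period | Covered | Uncovered | Uncovered share |
|---|---|---|---|---|
| Partners of male patients | 97 | 28 (28.9%) | 97 − 28 = 69 | 69/97 = 71.1% |
| Female patients | 35 | 28 (80.0%) | 35 − 28 = 7 | 7/35 = 20.0% |

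These are shares of calendar time, not of risk or of expected pregnancies.

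**Step 2. Is the gap closed elsewhere?** Section 8.1 keeps later serious adverse events reportable if the investigator learns of them. Section 8.8 treats outcomes such as spontaneous abortion, stillbirth, neonatal death and congenital anomaly as serious, so those could still be reported. A pregnancy is not in itself on the list of serious events in Section 8.4. Section 8.2 lists signs or symptoms resulting from exposure during pregnancy among possible adverse events, and non-serious events are recorded to the last visit or the start of new anticancer therapy. That covers signs and symptoms rather than the pregnancy, and does not clearly reach partners. No section extends the form itself past 28 days.

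**Step 3. Does the answer depend on what last treatment means?** If it meant surgery, coverage at the planned limit would end at 42 + 28 = 70 days after the last dose. The women's 35 days would then be covered, but 97 − 70 = 27 of the men's days would not. Section 8.1 ties its own 28 days to the last administration of the product, which favours counting from the last dose.

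**Step 4. How far would a longer trigger run past study exit?** With surgery *s* days after the last dose, the final visit falls at about day *s* + 30. For men the overrun is 97 − (*s* + 30) = 67 − *s* days. At the planned limit, *s* = 42, the visit is at about day 72 and the overrun is 25 days; it is longer if surgery is earlier. For women it is 35 − (*s* + 30) = 5 − *s* days, which is nil unless surgery comes within 5 days of the last dose. Day 72 is a planned limit, not a maximum: Section 9.2.4 has an endpoint counting delays to surgery beyond 6 weeks.

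**The case against.** The best reply is that a contraception requirement and an expedited-reporting trigger are different instruments and need not be equally long. The Section 4.2 text is an eligibility criterion about willingness to use contraception; it does not define an exposure or reporting period. That is fair, and it rules out saying that the protocol has declared a risk window and then failed to monitor it. The protocol uses no such term. But the reply does not explain why Section 8.8 defines exposure without a day limit and then requires reporting only to day 28. That tension lies within one section.

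A reader might also infer that most of the post-treatment period goes unreported for everyone. The documents support that only for partners of male patients; for women, 28 of 35 days are covered.

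Nor is it right that late pregnancies vanish from safety reporting. Serious outcomes known to the investigator remain reportable under Section 8.1, and pregnancy-related signs and symptoms may be recorded under Section 8.2. What is lost is chiefly the form and the required outcome follow-up for a late pregnancy with no serious event.

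Finally, the practical weight is small. There are 25 patients, and those unwilling or unable to use highly effective contraception are excluded. That stands, and it sets the priority of the point rather than removing it.

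**Conclusion.** The mismatch is real but minor. As written, the mandatory form covers the first 28 days only, leaving 69 of 97 days (71%) for partners of male patients and 7 of 35 days (20%) for female patients with no required pregnancy report or outcome follow-up.

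These figures assume that both periods run from the last dose. If the trigger ran from surgery at the planned limit, only the gap for men would remain, at 27 days. Confidence is high that the periods differ and that no other section extends the form. The number of pregnancies affected cannot be estimated from the protocol and is likely to be very small. The sample size, error rates and pCR analysis are untouched.

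**What to change.** Reconcile Sections 4.2, 8.1 and 8.8. The sponsor should confirm the post-treatment contraception period for each sex. The trigger in Section 8.8 should then cover any pregnancy beginning on treatment or before the end of that period, counted from the last dose, with the existing outcome follow-up attached. Section 8.1 should state that pregnancy reporting follows Section 8.8 and not the 28-day period for serious adverse events. Subjects should be told to notify the site of a pregnancy, their own or a partner's, within that period. Which contraception period is right is for the sponsor to decide.

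The cost is a sentence in Section 8.8, a cross-reference in Section 8.1 and an instruction to subjects. The real burden is passive reporting after study exit: with the present male period, about 25 days beyond a final visit at the planned limit, and longer if surgery is early. Because the synopsis has patients leave within 1 month of surgery and stops data collection on withdrawal, the protocol needs a stated exception for pregnancy reports, and the consent form may need a line to match.

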## **8.9 Withdrawal Due to Adverse Events**

Withdrawal due to an AE should be distinguished from withdrawal due to insufficient response, according to the definition of an AE noted earlier, and recorded on the appropriate AE CRF page.

When a subject withdraws due to a SAE, the SAE must be reported in accordance with the reporting requirements defined below.

## **8.10 Eliciting Adverse Event Information**

The investigator is to report all directly observed AEs and all AEs spontaneously reported by the study subject. In addition, each study subject will be questioned about AEs.

## **8.11 Reporting Requirements**

Each AE is to be assessed to determine if it meets the criteria for SAEs. If a SAE occurs, expedited reporting will follow local and international regulations, as appropriate. Adverse events should be reported using concise medical terminology on the CRF.

### **8.11.1 Serious Adverse Event Reporting Requirements**

For all SAEs, the investigator is obligated to pursue and provide information to drug provider in accordance with the timeframes for reporting. In general, this will include a description of the AE in sufficient detail to allow for a complete medical assessment of the case and independent determination of possible causality. Information on other possible causes of the event, such as concomitant medications and illnesses must be provided. In the case of a subject death, a summary of available autopsy findings must be submitted as soon as possible to the drug provider or its designated representative.

### **8.11.2 Non-Serious Adverse Event Reporting Requirements**

Non-serious adverse events should be recorded on the CRF from the time the subject has taken at least one dose of study treatment through last subject visit.

### **8.11.3 Reporting Requirements to Regulatory Authorities**

Adverse event reporting, including suspected serious unexpected adverse reactions, will be carried out in accordance with applicable local regulations.

## **9. DATA ANALYSIS/STATISTICAL METHODS**

Detailed methodology for summary and statistical analyses of the data collected in this study will be documented in a Statistical Analysis Plan (SAP), which will be dated and maintained by the investigator. This document may modify the plans outlined in the protocol; however, any major modifications of the primary endpoint and/or its analysis will also be reflected in a protocol amendment.

### **9.1 Sample Size Determination**

According to the Simon's 2-stage mini-max design, the null hypothesis that the PCR rate is  $\leq 10\%$  will be tested against a 1-sided alternative. In the first stage, 15 patients will be accrued. If there are 1 or fewer pCR in these 15 patients, the study will be stopped early for futility. Otherwise, 10 additional patients will be accrued for a total of 25. The null hypothesis will be rejected if 6 or more PCR are observed in 25 patients. This design yields a type I error rate of 0.05 and power of 0.80 when the true PCR rate is 30%.

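### The type I error is given as 0.05, but the stated two-stage rule has an exact one-sided rate of 0.033; 0.05 is only the ceiling used to select the design (minor, conservative)

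*Protocol*

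**What the plan says.** Protocol section 9.1 (Sample Size Determination) sets out the whole decision rule, and the Synopsis repeats it under the same heading.

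- Design family: "According to the Simon's 2-stage mini-max design".
- Null hypothesis: a pCR rate of 10% or less, which "will be tested against a 1-sided alternative".
- First stage: "In the first stage, 15 patients will be accrued".
- Futility: "If there are 1 or fewer pCR in these 15 patients, the study will be stopped early for futility".
- Second stage: "Otherwise, 10 additional patients will be accrued for a total of 25".
- Final decision: "The null hypothesis will be rejected if 6 or more PCR are observed in 25 patients".
- Operating characteristics: "This design yields a type I error rate of 0.05 and power of 0.80 when the true PCR rate is 30" per cent.

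Neither place calls 0.05 a nominal level, a target or an upper limit, and neither gives an attained type I error.

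**The concern.** The last sentence gives two figures as properties of the design, under a single verb. One of them, the power, is also the value the rule attains after rounding. The other, the type I error, is not. A reader cannot tell from the text that the first can be taken literally and the second only as a bound.

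This is the only hypothesis test in the protocol; sections 9.2.3 and 9.2.5 are otherwise descriptive. The figure is therefore the trial's one stated false-positive rate. Taken literally, it means a chance of 1 in 20 of declaring activity when the true rate is 10%; the actual chance is about 1 in 30. What is at stake is the accuracy of a reported operating characteristic, not how the trial is run.

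**Working it through.** **Inputs, all from section 9.1:** n1 = 15; stop if X1 ≤ 1; 10 further patients, N = 25; reject if the total is ≥ 6; null rate p0 = 0.10; alternative p1 = 0.30; one-sided.

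**Formula.** The trial rejects only if it passes the first stage (X1 ≥ 2) and reaches a total of 6:

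P(reject | p) = Σ over x = 2,…,15 of P(X1 = x) × P(X2 ≥ 6 − x), with X1 ~ Bin(15, p) and X2 ~ Bin(10, p).

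For x ≥ 6 the second factor is 1.

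**Step 1: the stated power (p = 0.30).**

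| x in first 15 | P(X1 = x) | P(X2 ≥ 6 − x) | product |
|---|---|---|---|
| 2 | 0.09156 | 0.35039 | 0.03208 |
| 3 | 0.17004 | 0.61722 | 0.10495 |
| 4 | 0.21862 | 0.85069 | 0.18598 |
| 5 | 0.20613 | 0.97175 | 0.20031 |
| ≥ 6 | 0.27838 | 1 | 0.27838 |
| **sum** | | | **0.8017** |

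The stated 0.80 reproduces.

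**Step 2: the stated type I error (p = 0.10).**

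| x in first 15 | P(X1 = x) | P(X2 ≥ 6 − x) | product |
|---|---|---|---|
| 2 | 0.266896 | 0.012795 | 0.003415 |
| 3 | 0.128505 | 0.070191 | 0.009020 |
| 4 | 0.042835 | 0.263901 | 0.011304 |
| 5 | 0.010471 | 0.651322 | 0.006820 |
| ≥ 6 | 0.002250 | 1 | 0.002250 |
| **sum** | | | **0.0328** |

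The stated 0.05 does not reproduce. To two decimals the attained rate is 0.03.

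**Step 3: does another reading of the rule give 0.05?**

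| Reading | Type I error at 10% |
|---|---|
| Rule as written (≥ 6, with futility stop) | 0.0328 |
| ≥ 6 of 25, futility stop ignored | 0.0334 |
| ≥ 5, with futility stop | 0.0933 |
| ≥ 5 of 25, futility stop ignored | 0.0980 |

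None does. The attainable values step from 0.033 to 0.093 as the cut-off moves from 6 to 5.

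**Step 4: where 0.05 comes from.** An exhaustive search over two-stage designs with p0 = 0.10, p1 = 0.30, type I error ≤ 0.05 and power ≥ 0.80 returns 1/15 and 5/25 as the minimax design. So 0.05 is the constraint on the search, and section 9.1 has the correct design for it.

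**Step 5: does a 0.05 criterion agree with the cut-off?**

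| Result | Exact one-sided p, two-stage rule | Exact one-sided p, stop ignored | Clopper-Pearson one-sided 95% lower bound |
|---|---|---|---|
| 6/25 | 0.0328 | 0.0334 | 0.110 (above 10%) |
| 5/25 | 0.0933 | 0.0980 | 0.082 (below 10%) |

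Both criteria reject at 6 and not at 5, exactly as the protocol's rule does.

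**Size of the gap:** 0.05 − 0.0328 = 0.0172 in absolute terms; 0.05 / 0.0328 = 1.52 as a ratio; 1 / 0.0328 ≈ 30.

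**The case against.** The best defence is that both figures are design parameters. A Simon design is specified by a null rate, an alternative rate, a type I error limit and a power target. Quoting the limit and the target is common shorthand, and a statistician who knows these designs will read 0.05 as a ceiling. The 0.80 is just as much a target, which the attained 0.8017 happens to round to. No cut-off at N = 25 attains 0.05, the discrepancy is on the safe side, and nothing in the conduct of the trial depends on it.

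Most of this stands, and it is why the point is minor. It does not rescue the sentence, which says what the design delivers and does not mention a limit. Read as written, the type I error figure is one that the rule does not have.

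Two stronger readings are tempting, and neither is supported.

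- *A reader might infer that the design or sample size is wrong.* It is not. The stage sizes, both boundaries and the power all reproduce, and the search in Step 4 returns this same design. There is no inflation of the type I error.
- *A reader might infer that a p-value or confidence level set at 0.05 would conflict with the decision rule.* It would not. Step 5 shows that a one-sided p-value and an exact one-sided 95% lower bound both reproduce the cut-off of 6. The 95% intervals for pCR in section 9.2.3 are a separate matter. The protocol neither ties them to the one-sided test nor names the method used for pCR, and restating the type I error would not change them.

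**Conclusion.** The stated type I error is inaccurate, and the point is minor. At a true pCR rate of 10% the exact one-sided rate of the rule is 0.033 (0.0328 with the futility stop, 0.0334 without it), against 0.05 in section 9.1 and the Synopsis. The design does keep the error below 0.05; it does not produce an error of 0.05. The difference of 0.017 is conservative, so a positive result is slightly stronger evidence against the null than the text implies.

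This rests on independent binomial outcomes, on exactly 15 and then 25 patients being counted, and on the boundaries being applied as written. If the futility stop were not enforced, the rate would still round to 0.033.

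**What to change.** In section 9.1 and in the Synopsis, replace the operating-characteristics sentence with: *one-sided type I error of at most 0.05 (exact 0.033 at a true pCR rate of 10%) and power of 0.80 at a true pCR rate of 30%*.

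The cost is one sentence in two places. Sample size, stage boundaries, cut-off and analysis do not change. The sponsor may also wish to give the probability of early stopping (0.55) and the expected sample size (19.5) at a true rate of 10%. That is optional, since the protocol misstates neither.
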